## RESEARCH PROTOCOL

## Hypothesis and aims.

Acute asthma produces greatly increased work of breathing and increased oxygen requirement secondary to bronchial narrowing and airway obstruction by inflammatory secretions. There is growing evidence that non-invasive ventilation can reverse these processes more efficiently than conventional asthma therapy. Surprisingly, there have not yet been any large scale prospective controlled studies to investigate this hypothesis, (either in adults or children). Consequently, the aim of this study is to determine if the use of non-invasive positive airway pressure, for children admitted to hospital with an acute exacerbation of asthma, reduces their work of breathing, need for adjunctive medications, and shortens the length of hospital stay, compared to current standard therapy.

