## **Research Methods:**

## Overview of study design:

The aim of the study is to determine if the use of NIV, for children admitted to hospital with an acute exacerbation of asthma, reduces their work of breathing, need for adjunctive medication, length of hospital stay, and need for intubation and mechanical ventilation. Study design will be prospective, randomized and controlled. The tightly fitting face mask necessary for NIV makes it impossible to make this a blinded study.

The principal enrollment criteria will be children over 2 years of age presenting to the ER with acute asthma. After diagnosis, all children are treated with standard therapy (systemic steroids plus 3 doses of inhaled salbutamol and 1 dose of inhaled ipratropium over a 1 hour period then hourly salbutamol). The principal decision between discharge track and admission track will be made at 2 hours after first steroid dose. Admission criteria are based on sequential PRAM scores.

After initial asthma treatment and observation in the emergency room, to determine which patients can be discharged home, those who need admission will be asked to join the study, then consented and randomized. There will be three treatment groups:

- BiPAP: standard steroid dose, hourly salbutamol and BiPAP at 15/5 cm H2O by face mask with rate 10 to 15/min, oxygen as needed.
- CPAP: standard steroid dose, hourly salbutamol and 8 to 10 cm H2O constant pressure by face mask, oxygen as needed.
- Conventional therapy: standard steroid dose plus hourly nebulized salbutamol, nebulized ipratropium q 6 hrly, magnesium sulphate 50 mg/kg IV (4 doses q 6 hrly), loading dose of aminophylline 6 mg/kg IV if no progress, oxygen as needed.

All children will be admitted to a small 3 bed respiratory unit. They will be closely monitored and objectively scored every 4 hours using the PRAM asthma clinical severity score (Pediatric Respiratory Assessment Measure)[18]. End points will be: time to reach room air, time to reach PRAM score <3, numbers requiring intubation and mechanical ventilation and medication use. Those children older than 5 or 6 yrs, will also perform lung function tests twice daily. Projected patient enrollment will be at least 30 in each arm. Estimated study duration is 6 months.

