#### Measured Outcomes:

- Length of time to reach a PRAM score of  $\leq 3$
- Time to room air.
- Total medication use per 12 hr period.
- Numbers failing treatment and transferred to ICU.
- Numbers in each group requiring hospital readmission within 48 hours of discharge
- Time to reach FEV1 >80% predicted in those children able to perform PFTs.

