#### Criteria for study termination:

- Failure to tolerate BiPAP (persistent agitation and tachycardia, refusal to wear mask) resulting in the need for its discontinuation despite appropriate administration of sedation.
- Signs of impending respiratory failure in either study arm should immediately prompt discussion with the ICU team and discontinuation of study participation

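### Length of stay is an aim with no end point, outcome or analysis; intubation is an end point that drops out of the outcome list and analysis; and the plan does not say that either is recorded once study participation is discontinued

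*Combined protocol and SAP*

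**What the plan says.** The aims appear twice. Hypothesis and aims gives three: whether the intervention "reduces their work of breathing, need for adjunctive medications, and shortens the length of hospital stay, compared to current standard therapy". The last of these, that it "shortens the length of hospital stay", is the one with no counterpart later in the plan. The Overview of study design gives four, the last three being "need for adjunctive medication, length of hospital stay, and need for intubation and mechanical ventilation". Intubation is therefore an aim only in the Overview.

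The Overview's end points are "time to reach room air, time to reach PRAM score <3, numbers requiring intubation and mechanical ventilation and medication use". Intubation is among them; length of stay is not.

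Measured Outcomes has six items and names neither. The nearest are "Numbers failing treatment and transferred to ICU" and "Numbers in each group requiring hospital readmission within 48 hours of discharge". The Statistical analysis text covers asthma score over time, time to the target score, drug treatments per 12 hours, and lung function.

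Two sections deal with children who get worse. General care for all three groups provides for medical review and ICU admission as needed, and does not mention leaving the study. Criteria for study termination requires discussion with the ICU team and "discontinuation of study participation" when respiratory failure appears imminent. Its other item concerns failure to tolerate BiPAP and speaks of stopping BiPAP, not of leaving the study.

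**The concern.** An aim with no outcome definition or analysis is not prespecified. For length of stay there is no clock start, no rule on whether ICU time counts, and no comparison method. The trial is unblinded and no discharge criteria are given, so a definition chosen after the data are seen would be open to challenge.

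The termination rule makes this more than a drafting gap. Imminent respiratory failure would normally come before intubation, and the children affected are likely to have the longest stays. If leaving the study also ends data collection, the loss depends on outcome. It could also differ by arm: the intolerance item names only BiPAP, and the deterioration item is worded as if there were two arms, although the trial has three. Outcome-dependent loss that differs by arm biases the comparison with control.

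**Working it through.** **1. The sections side by side**

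| Topic | Hypothesis and aims | Overview: aim | Overview: end point | Measured Outcomes | Statistical analysis |
|---|---|---|---|---|---|
| Work of breathing (through PRAM) | yes | yes | yes | yes | yes |
| Adjunctive medication | yes | yes | yes | yes | yes |
| Length of stay | yes | yes | no | no | no |
| Intubation | no | yes | yes | no | no |

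Length of stay is an aim and nothing else. Intubation gets as far as the Overview's end points and stops there. ICU transfer does not stand in for it, because a child can go to ICU without being intubated.

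**2. The two deterioration rules**

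General care: the child worsens, is reviewed and may go to ICU; study status is not mentioned. Termination criteria: respiratory failure threatens, the ICU team is consulted and participation ends. The same child can fall under both. No section says whether outcomes are recorded after participation ends, and none defines an analysis set of all randomised children.

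**3. The plan's own sample size**

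Inputs from Sample size calculation: 48 (SD 16) against 36 (SD 14) hours, power 80%, type 1 error 5% (two-sided assumed). The difference is 0.25 × 48 = 12 hours.

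n per arm = 2 × (1.96 + 0.8416)² × 16² / 12² = 27.9, so 28, against the stated 26. With the pooled SD, √((256 + 196)/2) = 15.03, a t test needs 25.6, so 26. The figure reproduces closely. It is sized on time to a PRAM of 3, not on stay or intubation.

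**4. What omitting failures could do to mean stay (assumed figures)**

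The documents give no failure rate and no stay for children who fail. Assume 30 per arm (the Overview's minimum), 48 hours for children who do not fail and 120 hours for those who do, with five failures in one arm and one in another.

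- All randomised: (25 × 48 + 5 × 120)/30 = 60.0 hours, and (29 × 48 + 1 × 120)/30 = 50.4 hours. Difference 9.6 hours.
- Failures omitted: 48 and 48 hours. Difference 0.

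In general, the hidden difference = (difference in number of failures)/30 × (extra hours per failure).

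| Difference in failures | 24 h extra | 48 h extra | 72 h extra |
|---|---|---|---|
| 1 | 0.8 | 1.6 | 2.4 |
| 4 | 3.2 | 6.4 | 9.6 |

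With equal failures and equal extra hours, nothing is hidden.

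**5. What intubation data could show at 30 per arm**

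The documents give no intubation rate, so a range of control rates is assumed. Power is for Fisher's exact test, two-sided 5%.

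| Control rate | Expected control events (30 × rate) | Power, rate halved | Power, rate falls to zero |
|---|---|---|---|
| 2% | 0.6 | about 0% | about 0% |
| 5% | 1.5 | 0.2% | 0.3% |
| 10% | 3.0 | 1.9% | 7.3% |
| 20% | 6.0 | 9.6% | 57% |

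An arm with no intubations among 30 children has an exact 95% upper limit of 1 − 0.025^(1/30) = 11.6%. Intubation can only be described at this size, but one or two lost events could be all that an arm has.

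**The case against.** A reader might infer that two of the four aims have no outcome and cannot be answered. The documents do not support that. Intubation is an explicit end point in the Overview, so its defect is a mismatch with Measured Outcomes and a missing analysis, not total absence. Ending participation need not end data collection: the plan is silent, and some of it points the other way. ICU transfers are counted, and these occur at or after deterioration. Readmission within 48 hours requires the discharge time, so stay could be derived from records.

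A reader might also infer that no intubation would ever be recorded. That follows only if every intubated child leaves first and goes uncounted, which assumes the conclusion. Nor does the plan propose analysing only children who complete; the arithmetic on mean stay shows what is at stake, not what is planned.

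Finally, adding intubation to the list will not give a useful test. Children already close to respiratory failure at presentation are excluded, and the arms are small.

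All of this stands, and it limits the claim. It does not remove the gap for length of stay, since a quantity that could be derived afterwards still has no prespecified definition or comparison. It also leaves the two deterioration rules unreconciled.

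**Conclusion.** The point holds in this form. One aim, length of stay, has no end point, outcome or analysis. Intubation is an aim and end point in the Overview only. Follow-up after discontinuation of participation is unstated, so a literal reading allows selective loss in the sickest children.

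The size of any bias cannot be taken from the documents. Under the assumed ranges, leaving out failures hides 0.8 to 9.6 hours of mean stay, against a design difference of 12 hours. That depends on failures being unequal between arms, failures staying longer, and their data not being used. The absence of length of stay from the outcomes and analysis rests on no assumption. The change should be made.

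**What to change.** Add two items to Measured Outcomes: (a) hours from randomisation to hospital discharge, including ICU time; and (b) intubation by discharge, carried over from the Overview and counted separately from ICU transfer.

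Reconcile General care for all three groups with Criteria for study termination. State that stopping the assigned treatment does not end data collection, and that all randomised children are followed to discharge and analysed in their assigned arm. This concerns data collection only; it leaves to the investigators when treatment is stopped.

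In Statistical analysis, prespecify the comparison of stay with control. A time-to-event method is one reasonable choice; others would serve if fixed in advance. Report intubation by arm as counts with exact confidence intervals, without a formal claim.

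The cost is two lines in the outcome list, two chart fields and no extra visits. The drawback is an intubation comparison with negligible power at about 30 per arm, which the plan should say openly.

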#### Study background.

Asthma is a common, chronic disorder of reversible airway obstruction caused by a triad of airway inflammation, bronchial smooth muscle contraction and increased airway secretions [1]. While there have been huge advances in the control of chronic childhood asthma, acute exacerbations remain common, particularly during the viral season. Acute asthma has a low mortality rate but the condition is so common that it imposes a very high health care burden. Studies by our own group [2] and others [3] have shown that asthma exacerbations remain a major cause of emergency room visits and a leading cause of hospitalization in children. The patient burden at Children's Hospital in Vancouver, is similar to published studies showing that asthma accounts for 3% to 7% of all pediatric ED visits with a mortality rate of 2 to 3 per million children in North America [3]. Any therapy that could improve the outcome in acute asthma would have significant medical and economic benefits.

There are two types of non invasive ventilation (NIV).[4] The first is continuous positive airway pressure (CPAP) where the patient breathes against a constant pressure delivered by face mask. The second is BiPAP – here the patient's breathing is assisted by cycling between high and low pressures at a pre-set rate. It is analogous to traditional ventilation but without the need for intubation. After its introduction around 1990, NIV rapidly gained acceptance in the treatment of a wide range of respiratory conditions[5]. Machines are relatively cheap and the non-invasive pressure delivery minimizes side effects compared to traditional ventilators. NIV is now the commonest form of ventilatory support used in intensive care units.

The standard therapy for acute asthma is based on oral or intravenous corticosteroids to control the acute inflammation plus a range of bronchodilators to reverse airway narrowing – the commonest of these is the beta agonist salbutamol. Most children admitted to hospital with acute asthma will improve with this well-established clinical framework [6]. A few children do not respond

However, a minority will not respond adequately to such management and require adjunctive medications, usually requiring admission to the ward, and sometimes to the ICU. Medical treatments commonly used in addition to beta agonists, include intravenous magnesium sulfate, inhaled anticholinergics and aminophylline. The evidence base for the efficacy of such treatments is limited and inconsistent, and adverse side effects are common [7].

There is growing evidence that positive airway pressure delivered by a non-invasive face mask, can reduce airway obstruction and also improve ventilation-perfusion mismatch. The resulting decrease in respiratory work and reduced need for added oxygen, shortens hospital stay and minimizes exposure to multiple medications [8]. In recent years the use of non-invasive positive pressure ventilation for management of a range of acute respiratory pathologies has become increasingly common. Results from studies in this area are encouraging, however most studies to date have been small and retrospective [9]. There is very little prospective controlled research to guide clinical practice concerning non-invasive ventilation in asthma. In view of the limited information available in the published literature, we believe that a prospective controlled trial of the value of BiPAP in acute asthma would provide a valuable evidence base to guide the management of this common clinical problem.

## Literature Review:

Although non-invasive ventilation is increasingly used for treatment of asthma in emergency medicine[10], there is surprisingly little relevant research literature. Recent literature reviews [9,11], including a Cochrane review based on only 5 studies[12], all conclude that the therapy is promising but that there is an urgent need for large controlled studies. Meduri, in adults[13] and Williams in children[14] published retrospective reviews of their clinical experience with non-invasive ventilation in acute asthma. Both claimed that non-invasive ventilation (NIV) was at least safe, and likely effective but neither included controls.

From a physiological point of view, there is good theoretical support for the use of NIV in acute asthma. The administration of positive pressure ventilation leads to bronchial distention and enables maintenance of small airway patency. This decreases airway resistance, recruits areas of atelectasis and facilitates clearance of secretions[15].

As noted, there have been very few prospective studies of NIV in the management of acute asthma. The addition of NIV to conventional therapy, in a small prospective adult study, showed significantly shorter ICU and hospital stays in the treatment arm[15]. A prospective randomized crossover study of 20 children with lower airway bstruction[16], reported a significant improvement in respiratory rate and clinical asthma score when receiving non-invasive ventilation, which worsened on conversion to standard medical treatment. A recent prospective randomized controlled pilot study [17] compared NIV to standard management in 20 patients with status asthmaticus. The study identified

significant improvements in respiratory rate and clinical asthma scores in the NIV treatment arm.

## **Research Methods:**

## Overview of study design:

The aim of the study is to determine if the use of NIV, for children admitted to hospital with an acute exacerbation of asthma, reduces their work of breathing, need for adjunctive medication, length of hospital stay, and need for intubation and mechanical ventilation. Study design will be prospective, randomized and controlled. The tightly fitting face mask necessary for NIV makes it impossible to make this a blinded study.

The principal enrollment criteria will be children over 2 years of age presenting to the ER with acute asthma. After diagnosis, all children are treated with standard therapy (systemic steroids plus 3 doses of inhaled salbutamol and 1 dose of inhaled ipratropium over a 1 hour period then hourly salbutamol). The principal decision between discharge track and admission track will be made at 2 hours after first steroid dose. Admission criteria are based on sequential PRAM scores.

After initial asthma treatment and observation in the emergency room, to determine which patients can be discharged home, those who need admission will be asked to join the study, then consented and randomized. There will be three treatment groups:

- BiPAP: standard steroid dose, hourly salbutamol and BiPAP at 15/5 cm H2O by face mask with rate 10 to 15/min, oxygen as needed.
- CPAP: standard steroid dose, hourly salbutamol and 8 to 10 cm H2O constant pressure by face mask, oxygen as needed.
- Conventional therapy: standard steroid dose plus hourly nebulized salbutamol, nebulized ipratropium q 6 hrly, magnesium sulphate 50 mg/kg IV (4 doses q 6 hrly), loading dose of aminophylline 6 mg/kg IV if no progress, oxygen as needed.

All children will be admitted to a small 3 bed respiratory unit. They will be closely monitored and objectively scored every 4 hours using the PRAM asthma clinical severity score (Pediatric Respiratory Assessment Measure)[18]. End points will be: time to reach room air, time to reach PRAM score <3, numbers requiring intubation and mechanical ventilation and medication use. Those children older than 5 or 6 yrs, will also perform lung function tests twice daily. Projected patient enrollment will be at least 30 in each arm. Estimated study duration is 6 months.

## Inclusion criteria:

In order to avoid confusion with viral bronchiolitis, the study is open to all children over 24 months old who present to the emergency department diagnosed with an acute asthmatic attack severe enough to require hospital admission.

## Diagnostic criteria:

The biggest challenge in asthma research is determining an unambiguous clinical definition that allows one coughing/wheezing child to be distinguished from another. Our group has recently published a large study of the best diagnostic indicators in tachypneic children[20]. Based on that work,our diagnosis of asthma will depend on respiratory rate greater than WHO's age-dependent criteria, a history of similar previous episodes and wheezing heard on auscultation by an experienced physician. These criteria provide a diagnostic sensitivity and specificity of 85%[20].

#### Exclusion criteria:

- Clinical suspicion of bacterial pneumonia: focal crackles or bronchial breathing, and/or major chest x-ray findings.
- Impending respiratory failure at presentation requiring direct PICU admission
- Any contraindication to BiPAP use including altered mental status, recent bowel surgery, intractable vomiting, inability to protect airway, pneumothorax.
- Receiving maintenance dose of oral steroid at time of hospital admission
- History of serious unrelated illness such as congenital heart disease or bronchopulmonary dysplasia.

#### Measured Outcomes:

- Length of time to reach a PRAM score of  $\leq 3$
- Time to room air.
- Total medication use per 12 hr period.
- Numbers failing treatment and transferred to ICU.
- Numbers in each group requiring hospital readmission within 48 hours of discharge
- Time to reach FEV1 >80% predicted in those children able to perform PFTs.

#### Study summary:

- Identify patients aged ≥ 2 years attending the Emergency Department with a significant acute asthma exacerbation (using criteria above).
- Begin steroids and initial protocolised standard bronchodilator therapy. Observe in ER and score PRAM hourly.
- Research coordinator is informed and provides parents and child with study information to read during the child's period of observation in the ED.
- A decision about study inclusion should be made 2 hours post-steroid administration in children with PRAM of 8 or more.
- Once admission decision has been made, child is eligible for the study. Obtain consent from the parents and assent from child where possible. If the child is too unstable, assent will be explained and collected when the child is capable.

• After consent, participants will be randomized to one of the three treatment arms in blocks of six, using consecutively numbered opaque envelopes stored in the ED.

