## Management of treatment groups:

Participants will be randomized into one of three treatment arms – BiPAP, CPAP, conventional therapy. In addition to standard therapy, the three treatments will consist of:

- BiPAP group (Trilogy device) to be started in the ER after randomization, pressures 16/5 cm H2O, with rate of 10 to 15 / minute plus hourly salbutamol.
- CPAP group (Trilogy device) to be started in ER after randomization. Starting pressure 8 cm H2O, increased to 10 cm H2O if no clinical response and hourly salbutamol.
- Conventional therapy, hourly nebulized salbutamol, nebulized ipratropium q 6 hrly, magnesium sulphate 50 mg/kg IV (4 doses q 6 hrly), loading dose of aminophylline 6 mg/kg IV if no progress.

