#### Study enrolment:

Parents will be approached while their child is receiving initial asthma therapy in the Emergency Room of the Post Graduate Institute of Paediatric Medical Research in Chandigarh, India. Parents will be approached by one of the two local study coordinators (both are qualified paediatricians), during the child's 2 hour observation period in the Emergency Department. At that time parents will be given the invitation letter, written in local language (Hindi) and the research coordinator will answer any questions they have. If they cannot read, the information will be read to them in a private room. If the child fails to improve and requires hospital admission, consent for study participation will be sought once the decision to admit has been made. This will not delay treatment in any way. Children will only be eligible to enroll in the study whilst they are in the Emergency

department. Previously admitted ward patients are not eligible. All study information and consent documents are attached in section 9.

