## Randomization:

Once consent has been obtained, treatment selection will be decided using consecutively numbered envelopes randomized in groups of six. These envelopes will be stored in a box in the Emergency Department. Once consent has been obtained, an envelope will be selected in numerical sequence to determine the child's allocated treatment group. The envelope will then be stapled to the consent form to enable the investigator to know each patient's subject study number.

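### A single disclosed block size of six in an open, single-unit trial lets the recruiting coordinators infer some upcoming allocations before consent, so selection could bias the comparison

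*Combined protocol and SAP*

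**What the plan says.** The Study summary allocates children to the three arms "in blocks of six, using consecutively numbered opaque envelopes stored in the ED". The Randomization section says that "treatment selection will be decided using consecutively numbered envelopes randomized in groups of six", drawn in number order from a box in the ED once consent is given, each then being stapled to the consent form. Neither section mentions varying block sizes, a list held away from the site, or withholding the block size from recruiters. No stratification is described, so there appears to be one running sequence.

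Four other statements matter here:

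- **Blinding** (Overview of study design): the mask "makes it impossible to make this a blinded study", and all children go to one 3-bed unit.
- **Recruitment** (Study enrolment): "Parents will be approached by one of the two local study coordinators", during the 2-hour observation period and so before consent.
- **Training** (Safety Monitoring): all research coordinators are trained in the protocol, which states the block size.
- **Follow-up** (General care for all three groups): the on-call research coordinator assesses the patients and records the data.

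**The concern.** An opaque envelope hides its own contents. It does not hide what the earlier envelopes in the block imply about it. Here the same people can know the block size, the position in the block (the envelopes are numbered in order) and the earlier allocations. As a block fills, the remaining options narrow, and near its end they can be fixed.

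That knowledge would be available before the family decides. A coordinator who expects an NIV slot could press less hard with a family whose child seems unlikely to tolerate a mask, or more hard when conventional care is due. Entry leaves some discretion: the Statistical analysis section accepts that PRAM is partly subjective, and one exclusion rests on clinical suspicion of pneumonia. With about 30 children per arm, steering a few of them could make the arms differ at baseline.

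**Working it through.** The plan gives no figure for predictability, so there is none to reproduce.

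**Inputs**
- Block size 6, fixed (Study summary; Randomization).
- Three arms: "Participants will be randomized into one of three treatment arms" (Management of treatment groups).
- Planned size: "Projected patient enrollment will be at least 30 in each arm" (Overview of study design), so 90 children, or 90/6 = 15 blocks.
- Assumption: two children per arm in each block. The documents say only six; equal planned arms make 2:2:2 the natural reading.
- Assumption: the observer knows the block size and every earlier allocation. This gives the upper bound. An observer who tracks nothing has 0% certainty and a 33.3% guess rate.

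**Allocations known with certainty**
- 6th in the block: always known.
- 5th: known if the two remaining envelopes are the same arm, probability 3/15 = 1/5.
- Positions 1 to 4: never.
- Total (1 + 1/5)/6 = 1.2/6 = 20%, or 15 × 1.2 = 18 of 90. At the 26 per arm of the sample size section (78 children, 13 blocks) it is 13 × 1.2 = 15.6.

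**Conventional care versus NIV known with certainty**
- The next child must be NIV at position j if both conventional slots are already used: C(j−1, 2)/C(6, 2). For j = 3, 4, 5, 6 this is 1/15, 3/15, 6/15, 10/15. The sum is 20/15, and (20/15)/6 = 22.2%, or 20 of 90.
- The next child must be conventional if all four NIV slots are used: 1/15 at j = 5 and 5/15 at j = 6. The sum is 6/15, and (6/15)/6 = 6.7%, or 6 of 90.
- Together 26/90 = 28.9%. This figure needs only the position in the block and whether earlier children wore a mask.

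**Best guess of the arm**

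| Position | Success rate | Reason |
|---|---|---|
| 1 | 1/3 | no information |
| 2 | 2/5 | an unused arm has 2 of the 5 left |
| 3 | 1/2 | the commonest remaining arm has 2 of the 4 left |
| 4 | 2/5 × 1/3 + 3/5 × 2/3 = 8/15 | one of each left, or a 0/1/2 split |
| 5 | 1/5 × 1 + 4/5 × 1/2 = 3/5 | two alike, or two different |
| 6 | 1 | one left |

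The mean is (0.333 + 0.400 + 0.500 + 0.533 + 0.600 + 1)/6 = 3.367/6 = 56.1%, against 33.3% by chance. That is about 50 correct guesses of 90, against 30.

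**With randomly varied block sizes** (simulated trials of 90 children; the guesser knows the possible sizes but not the current one)

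| Block sizes | Known with certainty | Best-guess success |
|---|---|---|
| 6 only | 20% | 56% |
| 3, 6, 9 | about 4% | about 55% |
| 6, 9, 12 | about 2% | about 52-53% |

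**The case against.** The strongest defence is that the plan already limits discretion. The decision point is set at 2 hours after steroid in children with PRAM at or above 8. Children needing direct PICU admission or with a contraindication to BiPAP are excluded from every arm. Consent comes before the envelope, envelopes are taken in order, and stapling each to the consent form leaves an audit trail. This stands in part: it makes reversal after opening difficult and narrows the room for steering. It does not govern how a family is approached or persuaded before consent.

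Several stronger readings are tempting, and the documents do not support them:

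- **That coordinators can work out every allocation.** Full certainty covers at most one in five; the rest is guessing at better than chance.
- **That seeing the mask reveals the arm.** BiPAP and CPAP both use a face mask and the same device, so a mask separates NIV from conventional care only. Telling the three arms apart relies on the coordinators' role in assessing patients and recording data.
- **That the comparison is biased.** The documents show an opportunity. Whether anyone would use it, and its effect on time to PRAM of 3, cannot be calculated from them.
- **That no analysis could help.** PRAM is scored hourly in the ER before randomisation, so measured severity could be adjusted for. Unmeasured factors such as expected mask tolerance could not.

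**Conclusion.** The weakness is real but limited. One disclosed block size, open treatment and recruiters who can know the earlier allocations make part of the sequence predictable before consent. At most, 20% of allocations are certain, 29% are certain as to conventional care versus NIV (22% must be NIV, 7% must be conventional), and the best guess succeeds 56% of the time. NIV versus conventional care matters most here, because the Statistical analysis section compares each NIV arm with conventional care.

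The figures rest on the unstated 2:2:2 composition and on a coordinator who tracks every allocation. The arithmetic is firm under those assumptions; the step from predictability to bias is a possibility only. This does not invalidate the trial. It merits correction because blinding is not available and the remedy is cheap.

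**What to change.** Have someone independent of recruitment prepare the list off-site with randomly varied block sizes, for example 6, 9 and 12. Remove the block size from the Study summary and Randomization sections of the protocol held by site staff, and keep the sizes only in a document held by the list-maker.

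The cost is one new list, a new set of envelopes and a wording change in two sections; final arm sizes may differ by a few children. If enrolment has begun, the change can protect only the allocations still to come. The benefit is mainly the removal of certainty. Guessing at better than chance remains, so the change reduces the problem without ending it. Clinical care is unaffected.
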